10.3.5. Other Analyses

10.3.5.1. Health Economics

Summary statistics, including number of patients and proportion of categorical outcomes (5 levels) for the 5 dimensions (mobility, self-care, usual activity, pain/discomfort, and anxiety/depression) of the EQ-5D-5L will be provided by visit and by treatment. The change

from baseline to LOCF endpoint (Week 26, Visit 18) in the EQ-5D-5L UK population-based health state index score and EQ VAS score will be analyzed using the ANCOVA model described in Section 10.3.1.

For the ITSQ, the change from baseline to LOCF endpoint while on treatment in each domain transformed score (inconvenience, lifestyle, hypoglycemic control, glycemic control, delivery system) and overall transformed score will be analyzed using the ANCOVA model described in Section 10.3.1.

For the WPAI-GH, the change from baseline to LOCF endpoint in each score (absenteeism, presenteeism, work productivity loss, and activity impairment) will be analyzed using the ANCOVA model described in Section 10.3.1.

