- q Serum pregnancy test must be performed in women of childbearing potential at Visit 1 followed by a urine pregnancy test within 24 hours prior to IP exposure at randomization (Visit 8) and at other times at the investigator's discretion. When required per local regulations and/or institutional guidelines, local pregnancy testing will occur at mandatory times during the study treatment period.
- r Follicle-stimulating hormone test must be performed at Visit 1 for a postmenopausal woman who is between 50 and 54 years of age (inclusive) with an intact uterus, not on hormone therapy, and who has had at least 6 months of spontaneous amenorrhea.
- s Pharmacogenetic sample can be collected at any other visit if not collected at Visit 8.
- t Patients with treatment-emergent insulin lispro antibodies measured at Visit 801 that have not returned to prespecified baseline range (Visit 2), will be asked to undergo additional antibody monitoring as described in [Appendix 8](#). This follow-up assessment also applies to any patient who discontinues study insulin treatment prior to the end of the planned treatment period who has a treatment-emergent antibody response that has not returned to baseline range by Visit 801. It is recommended that the first insulin lispro antibody follow-up visit (Visit 802) be scheduled for all study patients, regardless of treatment-emergent antibody status.
- u Health outcomes questionnaires will be administered at the study sites based on the availability of appropriate translations. The questionnaires should be administered prior to other study procedures except at Visit 8 and Visit 18 when questionnaires may be administered following the start of the MMTT.

3. Introduction

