5.3.1. Safety Follow-Up Period

Safety follow-up visit guidelines are as follows (Section 2):

- For patients who discontinue from the study early during the lead-in period (prior to randomization), only an early discontinuation visit should be completed.
- For patients who discontinue from investigational product (IP) early but remain in the study, all remaining visits should be completed per Schedule of Activities.
- For patients who discontinue from the study early (regardless of whether they discontinue IP at the same time or have discontinued IP at an earlier visit), an early discontinuation visit followed by the safety follow-up visit (Visit 801) should be completed as per the Schedule of Activities.
- For patients who finish Visit 18 without early discontinuation of IP, a safety follow-up visit should be completed 4 weeks after Visit 18.

All patients who complete the 4-week safety follow-up visit (Visit 801) and have treatment-emergent insulin lispro antibodies that have not returned to prespecified baseline range (Visit 2) will be asked to participate in follow-up to monitor insulin lispro antibody levels as described in [Appendix 8](#). Patients participating in the antibody follow-up period will complete the study when insulin antibodies have returned to baseline range or when Visit 803 is completed, whichever occurs first.

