The definitions of baseline and post-baseline for the efficacy and safety analyses depend on which analysis period is being used. The following analysis periods will be used:

- Lead-in Period – Visits 2 to 8
- 26-Week Treatment Period – from randomization to Week 26 prior to discontinuation of IP and from randomization to Week 26 (including all data regardless of IP use)
- 26-Week Treatment Period and Safety Follow-Up Visit – from randomization to Visit 801 (including all data regardless of IP use)

The data on IP is defined based on the following rules:

- For data only measured at an office visit
 - MMTT postbaseline data will be classified as on IP if the MMTT performance date is prior to or on the last IP dose date
 - Other postbaseline data (for example, vital signs, safety laboratory tests, and questionnaires) will be considered as on IP if the measurement was performed at or prior to the cutoff date defined as 14 days after the last IP dose date
- For data collected as running records with an exact date stamp such as adverse events (AEs) and diary entries where the dates of the measures were not tied with the date of an office visit, postbaseline data with dates \leq (last study drug dose date +1) will be considered as data on IP.

Table 6.2 describes the rules for determining the patient population, baseline and postbaseline observations for the different analysis periods.

For continuous measures, summary statistics will include sample size, mean, SD, median, minimum, and maximum for both the actual and the change from baseline measurements. Least-squares (LS) means and standard errors derived from the analysis models will also be displayed. Treatment comparisons will be displayed showing the treatment difference LS means and the 95% CIs for the treatment differences, along with the p-values for the treatment comparisons.

For categorical measures, summary statistics will include sample size, frequency, and percentages. Fisher's exact test or Pearson's chi-square test will be used for treatment comparisons.

For laboratory values, both conventional (CN) and Systeme International (SI) units will be presented. Therefore, both % and mmol/mol will be presented for HbA1c and both mg/dL and mmol/L will be presented for glucose measurements.

All baseline measures will be analyzed using an analysis of variance (ANOVA) model that has treatment as the model term.

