Study Period/Analysis	Patient Population	Baseline Observations	Post-Baseline Observations
1,5-AG	All Randomized Patients with a baseline and at least one post-baseline observation	Visit 8 prior to initiation of IP	Visits 11, 15, and 18 prior to discontinuation of IP AND Last of Visits 9-18 prior to discontinuation of IP
Health outcomes: ITSQ, EQ-5D-5L, EQ-VAS, WPAI-GH	All Randomized Patients with a baseline and a post-baseline observation	Last of Visits 1-8	Last of Visits 9-18 prior to discontinuation of IP
Safety Laboratory Tests (chemistry, hematology, lipids) – continuous analysis	All Patients in the Safety Population with a baseline and a post-baseline observation	Last of Visit 1-8	Visit 18 (planned) AND last of Visits 9-18 (planned including early discontinuation visits) regardless of IP use
Safety Laboratory Tests (chemistry, hematology, lipids) – categorical analysis	All Patients in the Safety Population with a normal baseline (with respect to the direction being analyzed) and a post-baseline observation	Visits 1-8 (including unplanned tests)	Visits 9-18 (including unplanned tests) regardless of IP use
TEAEs	All Patients in the Safety Population	Prior to first dose of randomized IP (or Visit 8 date if the dose date is missing) but after the first dose of open-label insulin lispro in the Lead-in Period	From first dose of randomized IP to last dose of randomized IP AND From first dose of randomized IP to Visit 801
Hypoglycemia events	Safety Population	All Visits 2-8	All Visits 9-18 prior to discontinuation of IP
Weight and vital signs	All Patients in the Safety Population with a baseline and a post-baseline observation	Last of Visits 2-8	Visits 9-18 prior to discontinuation of IP AND Visits 9-801 regardless of IP use
Anti-insulin lispro antibodies	Safety Population	Visit 2	Visits 3-801 regardless of IP use

Abbreviations: 1,5-AG = 1,5-Anhydroglucitol; ANCOVA = analysis of covariance; EQ-5D-5L = European Quality of Life - 5 Dimensions 5 Level; EQ-VAS = EuroQol visual analogue scale; HbA1c = hemoglobin A1c; IP = investigational product; ITSQ = Insulin Treatment Satisfaction Questionnaire; ITT = intention-to-treat; LOCF – last-observation-carried forward; MMTT = mixed meal tolerance test; MMRM = mixed-effect model repeated measures; PPG = postprandial glucose; SMBG = self-monitored blood glucose; TEAE = treatment-emergent adverse event; WPAI-GH = Work Productivity and Activity Impairment General Health.

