6.11.5. Other Secondary Efficacy Analyses

The analyses described in Section 6.11.5 to Section 6.11.7 will include data collected from all randomized patients prior to permanent discontinuation of IP. The longitudinal observations of actual and change from baseline in HbA1c up to Week 26 will be analyzed using the same MMRM model as for the analysis of the primary outcome. For the following secondary efficacy endpoints, an MMRM model similar to that for the primary outcome with an additional term of HbA1c stratum ($\leq 8\%$, $> 8\%$) will be used:

- actual and change from baseline 1,5-AG values
- actual and change from baseline 10-point SMBG values (fasting, 1 hour post morning meal, 2 hours post morning meal, pre midday meal, 1 hour post midday meal, 2 hours post midday meal, pre evening meal, 1 hour post evening meal, 2 hours post evening meal, and bedtime)
- actual and change from baseline in total, basal, and prandial insulin doses and prandial/total insulin dose ratios

Three 10-point SMBG profiles are expected to be collected during the 2 weeks prior to specified visits. Valid SMBG profiles will be used for analysis, defined as having non-missing values at ≥ 6 time points among the 10 pre-specified time points and being collected during 2 weeks prior to a given visit. For each time point, the average of the corresponding SMBG values from the valid SMBG profiles will be used for analysis. The excursion of SMBG for each meal category (that is, morning meal, midday meal, and evening meal) calculated using the average values at the corresponding time points will be used for analysis.

The following endpoints, collected from the MMTT, will be analyzed using the ANCOVA model with strata (pooled country, type of basal insulin, number of prandial doses at study entry, and HbA1c stratum) and treatment as fixed effects and baseline as a covariate:

- actual and change from baseline in fasting glucose (average of measurements at time -15 and 0), and PPG at 15, 30, 60, 120, 180, and 240 minutes after the meal
- PPG excursions at time 15, 30, 180, and 240 minutes after the meal (PPG minus fasting glucose)

Sensitivity analysis for PPG excursions may be performed to exclude patients whose PPG excursion could be affected by factors including MMTT consumption amount (for example, partial MMTT was consumed) and correction bolus insulin usage.

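### After baseline the questionnaires are collected only at Visit 18 and at study withdrawal, so patients who stop IP more than 14 days before Visit 18 and stay have no on-treatment score to carry forward

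*Protocol*

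**What the plan says.** Objective 11 (ITSQ) is an other secondary objective; objectives 15 (EQ-5D-5L) and 16 (WPAI-GH) are exploratory.

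- **Endpoint.** Protocol 10.3.5.1 has, for ITSQ, "For the ITSQ, the change from baseline to LOCF endpoint while on treatment in each domain transformed score". Its text on EQ-5D-5L and WPAI-GH speaks of an LOCF endpoint without the on-treatment qualifier.
- **Data used.** The SAP applies the on-IP restriction to all three. The health outcomes row of Table 6.2 takes "Last of Visits 9-18 prior to discontinuation of IP", in "All Randomized Patients with a baseline and a post-baseline observation". SAP 6.11.5 adds: "The analyses described in Section 6.11.5 to Section 6.11.7 will include data collected from all randomized patients prior to permanent discontinuation of IP".
- **On IP.** SAP 6.1 counts a questionnaire as on IP up to the "cutoff date defined as 14 days after the last IP dose date".
- **LOCF.** Protocol 10.3.1 carries forward post-baseline values only, so baseline cannot stand in.
- **Collection.** The Schedule of Activities marks each questionnaire at Visits 2, 8 and 18 and at ED. Footnote u confirms the late visit: "except at Visit 8 and Visit 18 when questionnaires may be administered following the start of the MMTT". Nothing is scheduled at Visits 9 to 17.
- **Who has an ED visit.** Protocol 5.3.1 states: "For patients who discontinue from investigational product (IP) early but remain in the study, all remaining visits should be completed per Schedule of Activities". It assigns the ED visit to patients who leave the study, and 8.2 agrees. Section 8.1 encourages patients who stop IP to stay.

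**The concern.** An on-treatment LOCF endpoint suggests that a patient who stops IP contributes the last rating given on it. That needs at least one post-baseline rating before the stop, and for these instruments none is scheduled. HbA1c is different: Table 6.2 uses on-IP values at Visits 11, 13, 15 and 18, so a patient who stops midway still contributes.

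The rule also treats two kinds of stopper differently. Those who stop and leave promptly can contribute an ED score. Those who stop and stay, as the protocol encourages, cannot. Inclusion thus depends on behaviour after randomization that could be related to the outcome, most obviously for treatment satisfaction. The stress test for missing data in SAP 6.11.4 covers only the primary endpoint, so it would not show any effect here.

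**Working it through.** **1. Trace by type of patient**

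| Patient | Post-baseline questionnaire | On IP under SAP 6.1? | In the analysis? |
|---|---|---|---|
| Completes on IP | Visit 18 | Yes | Yes |
| Stops IP within 14 days before Visit 18, stays | Visit 18 | Yes | Yes |
| Stops IP more than 14 days before Visit 18, stays | Visit 18 | No | No |
| Stops IP, leaves, ED within 14 days of last dose | ED | Yes | Yes, if ED counts within Visits 9-18 |
| Stops IP, stays a while, leaves more than 14 days after last dose | ED | No | No |

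The condition in the fourth row arises because Table 6.2 says that early discontinuation visits count for continuous laboratory analyses but does not say so for questionnaires.

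**2. Share of those who stop and stay with no usable value**

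Visit 18 is at day 26 × 7 = 182. The cut-off falls at 182 − 14 = day 168. The documents give no stopping times, so assume the share stopped by day t is (t/182)^h. The share lost is then (168/182)^h:

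- h = 0.5 (early stopping): 96%
- h = 1 (uniform): 92%
- h = 2: 85%
- h = 4 (late stopping): 73%

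Most of this group is lost under each shape.

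**3. Number of patients**

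The plan states no figure for this group. The nearest is 670 randomized and 568 completing: 670 − 568 = 102, or 102/670 = 15.2%. The Synopsis and 5.2 describe the 568 as completing treatment; 10.1 describes them as completing the study. On the second wording, patients who stop IP and stay would be among the 568, so 102 is not a bound. For illustration, take all 102 as IP stoppers, assume a share s stays, and use uniform stopping. The number lost is 102 × s × 168/182:

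| s (assumed) | Patients lost | % of 670 |
|---|---|---|
| 10% | 9 | 1.4 |
| 25% | 24 | 3.5 |
| 50% | 47 | 7.0 |
| 100% | 94 | 14.1 |

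**4. What this could do to the comparison**

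If a proportion p of an arm is excluded and their unseen on-treatment score lies g points below that of the retained patients, the retained mean is too high by p × g. The between-arm bias is p₁g₁ − p₂g₂, which is zero when rate and reason match. With a common g it is (p₁ − p₂) × g. All inputs below are assumptions: a rate difference of 2 to 4 percentage points, g of 10 to 20 on the 0-100 scale, SD 20, 300 per arm.

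- Bias: 0.02 × 10 = 0.2 to 0.04 × 20 = 0.8 points.
- SE: 20 × √(2/300) = 1.63.
- Bias in SE units: 0.2/1.63 = 0.12 to 0.8/1.63 = 0.49.
- Two-sided false-positive rate: about 5.2% to about 8%, against a nominal 5%.

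The upper end needs the least favourable value of both the rate difference and g. If stoppers scored no lower, or higher, the bias would vanish or reverse.

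**The case against.** The best defence is that the restriction is declared. Protocol 10.3.1 assigns other secondary and exploratory efficacy objectives to the efficacy estimand unless otherwise specified, SAP 6.11.5 repeats it, and Table 6.2 asks for a post-baseline observation. Nowhere does the plan promise that every IP stopper contributes. This stands. The choice of an on-treatment question is not at fault; the collection schedule leaves that question without data for one group.

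For ITSQ, excluding the off-IP Visit 18 score is also right. The instrument rates satisfaction with insulin treatment (protocol 9.9.2), and protocol 7.8.2 sends patients who stop IP back to their prestudy prandial insulin or to another analog. Their Visit 18 score does not rate the blinded study insulin. This stands too: an all-data analysis cannot recover the missing on-treatment satisfaction.

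The group may be small. The SAP has a fallback imputation for the primary analysis in case few patients stop IP and complete the study. With double-blind arms at the same lispro concentration, a 4-point difference in the rate of stopping and staying (0.04 × 335, about 13 patients in an arm) is not an obvious default. This limits the likely size but does not supply the missing scores.

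Three points weigh on the detail. In the protocol the on-treatment wording is attached only to ITSQ, so objectives 15 and 16 are caught through the SAP. Part of SAP 6.3, on dropouts, is blacked out, so a provision there cannot be excluded. And the SAP version in hand already draws on blinded counts of randomized patients, so a schedule change cannot reach patients who have already stopped.

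**Conclusion.** The gap is real and follows from the documents' own rules. Patients who stop IP more than 14 days before Visit 18 and remain in the study have no eligible value for objectives 11, 15 and 16, while those who stop and leave promptly can have one. That this is most of the stop-and-stay group (73% to 96%) rests on assumed timing. The number of patients and the size and direction of any bias are unknown, because the documents give no rate of stopping and staying.

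A reader might infer that every patient who stops IP is lost; the 14-day rule and the ED visit say otherwise. A reader might infer that satisfaction is overstated in both arms, or that the comparison favours the arm losing more dissatisfied patients. The documents do not support that: protocol 8.1.1 also lists pregnancy, unblinding, prohibited medication and more than 14 consecutive days without IP as reasons to stop, and if stopping is balanced in rate and reason there is no between-arm bias. Nor do the primary or multiplicity adjusted objectives come into question; these endpoints are secondary or exploratory and outside the testing scheme. This is a cheap improvement to make, not a threat to the main conclusions.

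**What to change.** **1. SAP Table 6.2 and 6.11.7, no new data.**

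- Beside the planned on-IP analysis, add a supplementary ANCOVA for EQ-5D-5L and WPAI-GH on all Visit 18 and ED questionnaires regardless of IP use.
- State in the questionnaire row that ED visits count.
- Report, per arm, how many randomized patients are excluded from each questionnaire analysis, ITSQ included, for want of an on-IP value. That count shows whether the gap matters.
- Do not use off-IP Visit 18 ITSQ scores as ratings of the study insulin.

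**2. Schedule of Activities and protocol 5.3.1, if the schedule can still be changed.** Have randomized patients complete the questionnaires at permanent IP discontinuation, within the existing 14-day window. This is the only route to an on-treatment ITSQ value for those who then stay, and it makes LOCF work as described.

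**Cost.** The first change takes SAP wording, one more run of existing models and a count. Its result answers a treatment-policy question and must be labelled as such beside the on-treatment result. The second takes a schedule footnote and one extra self-completed set for patients who stop IP.

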10.3.5.2. Subgroup Analyses

The following subgroups will be analyzed using the efficacy estimand to evaluate consistency of treatment effects on the primary efficacy measure if there are sufficient numbers of patients in each treatment by subgroup (for example, 10%):

- Age (<65, ≥65 years and <75, ≥75 years and <65, ≥65 to <75, ≥75 to <85, ≥85 years)
- HbA1c stratum (≤8.0%, >8.0%)
- Sex (male or female)
- BMI (<25, ≥25 kg/m² and <30, ≥30 kg/m² and <35, ≥35 kg/m²)
- Duration of diabetes (using the median as the cut-off)
- Race
- Ethnicity
- Country
- Region
- Baseline 1-hour PPG excursion
- Baseline 1-hour PPG (PPG ≤180 mg/dL, >180 mg/dL)
- Baseline 2-hour PPG excursion
- Baseline 2-hour PPG (PPG ≤180 mg/dL, >180 mg/dL)
- Prandial insulin dosing plan (carbohydrate counting, pattern adjustment)
- Type of basal insulin during the lead-in period (glargine, degludec)
- Number of prandial doses at study entry (<3, ≥3)
- SGLT-2 inhibitor treatment

Analyses for HbA1c and change from baseline in HbA1c will be performed using an MMRM model that includes the same fixed effects given for the primary analysis model plus factors of subgroup, 2-way interaction of subgroup and treatment, 2-way interaction of subgroup and visit, and 3-way interaction of treatment, visit and subgroup. The interaction of subgroup and treatment at the primary endpoint (Week 26) will be evaluated to assess the treatment by subgroup interaction. When analyzing HbA1c stratum (≤8.0%, >8.0%) as a subgroup, the baseline HbA1c will not be included as a covariate to avoid confounding.

Additional subgroup analyses may also be performed.

Appendix 1. Abbreviations and Definitions

Term	Definition
1,5-AG	1,5-Anhydroglucitol
AE	adverse event: Any untoward medical occurrence in a patient or clinical investigation subject administered a pharmaceutical product and that does not necessarily have a causal relationship with this treatment. An adverse event can therefore be any unfavorable and unintended sign (including an abnormal laboratory finding), symptom, or disease temporally associated with the use of a medicinal (investigational) product, whether or not related to the medicinal (investigational) product.
ALP	alkaline phosphatase
ALT	alanine aminotransferase
ANCOVA	analysis of covariance
ANOVA	analysis of variance
AST	aspartate aminotransferase
BG	blood glucose
blinding/masking	
A single-blind study is one in which the investigator and/or his staff are aware of the treatment but the patient is not, or vice versa, or when the sponsor is aware of the treatment but the investigator and/his staff and the patient are not.
 
A double-blind study is one in which neither the patient nor any of the investigator or sponsor staff who are involved in the treatment or clinical evaluation of the patients are aware of the treatment received.

BMI	body mass index
CI	confidence interval
Product complaint	Product complaints are a customer's written, electronic, or oral communication that alleges deficiencies related to the identity, quality, durability, reliability, safety, effectiveness, or performance of a Lilly product after it is released for distribution.
CRP/CRS	clinical research physician: Individual responsible for the medical conduct of the study. Responsibilities of the CRP may be performed by a physician, clinical research scientist, global safety physician, or other medical officer.
CSII	continuous subcutaneous insulin infusion
CSR	clinical study report
ECG	electrocardiogram
eCOA	electronic clinical outcomes assessment

eCRF	case report form
enroll	The act of assigning a patient to a treatment. Patients who are enrolled in the trial are those who have been assigned to a treatment.
enter	Patients entered into a trial are those who sign the informed consent form directly or through their legally acceptable representatives.
EQ-5D-5L	European Quality of Life – 5 Dimensions 5 Level
ERB	ethical review board
FBG	fasting blood glucose
FDA	Food and Drug Administration
GCP	good clinical practice
GD	glucodynamic(s)
GRAS	Generally Recognized As Safe
HbA1c	hemoglobin A1c
IB	Investigator’s Brochure
ICF	informed consent form
ICH	International Conference on Harmonisation
IP	investigational product: A pharmaceutical form of an active ingredient or placebo being tested or used as a reference in a clinical trial, including products already on the market when used or assembled (formulated or packaged) in a way different from the authorized form, or marketed products used for an unauthorized indication, or marketed products used to gain further information about the authorized form.
ITSQ	Insulin Treatment Satisfaction Questionnaire
ITT	intention to treat: The principle that asserts that the effect of a treatment policy can be best assessed by evaluating on the basis of the intention to treat a patient (that is, the planned treatment regimen) rather than the actual treatment given. It has the consequence that patients allocated to a treatment group should be followed up, assessed, and analyzed as members of that group irrespective of their compliance to the planned course of treatment.
IV	intravenous
IWRS	interactive web-response system
LLT	lowest level term
LOCF	last observation carried forward
LS	least squares

MAR	missing at random
MDI	multiple daily injection
MedDRA	Medical Dictionary for Regulatory Activities
MMRM	mixed-effect model repeated measure
MMTT	mixed-meal tolerance test
NIM	noninferiority margin
NPH	neutral protamine Hagedorn
OAM	oral antihyperglycemic medication
PK	pharmacokinetic(s)
PP	per protocol
PPG	postprandial glucose
PT	preferred term
RBA	radio ligand-binding assay
SAE	serious adverse event
SAP	statistical analysis plan
screen	The act of determining if an individual meets minimum requirements to become part of a pool of potential candidates for participation in a clinical study.
SC	subcutaneous
SD	standard deviation
SMBG	self-monitored blood glucose
SOC	system organ class
SUSARs	suspected unexpected serious adverse reactions
T1D	type 1 diabetes
T2D	type 2 diabetes
TBL	total bilirubin level
TEADA	treatment-emergent anti-insulin lispro antibody

TEAE	treatment-emergent adverse event: An untoward medical occurrence that emerges during a defined treatment period, having been absent pretreatment, or worsens relative to the pretreatment state, which and does not necessarily have to have a causal relationship with this treatment.
ULN	upper limit of normal
URI	ultra-rapid insulin
VAS	visual analog scale
WPAI-GH	Work Productivity and Activity Impairment Questionnaire General Health

